T2DM is associated with an elevated risk of cardiovascular morbidity and mortality as well as renal failure. The cardiovascular benefit of SGLT2 inhibition was demonstrated in the EMPA-REG study by showing a lower rate of the primary composite cardiovascular outcome and of death in the active empagliflozin treatment arm (Zinman et al, 2015 [3]). There is also a growing body of evidence indicating that SGLT2 inhibition is nephroprotective. Post-hoc analysis from the dapagliflozin phase II and phase III programme have shown in T2DM patients with moderate renal impairment on top of renin-angiotensin-aldosterone system (RAAS) blockade reduction around 40% in albuminuria and stabilization of eGFR decline for up to 1 year (Sjöström et al, 2015 [4]) and 2 years (Fioretto et al, 2015 [5]). After an initial drop in eGFR, kidney function was stable over time while a progressive decrease in eGFR was seen in the placebo group. In another trial with the SGLT2 inhibitor empagliflozin, a 38%, 44% and 55% risk reduction was found in new onset of macroalbuminuria, doubling of serum creatinine and initiation of dialysis treatment respectively. Moreover, the overall risk reduction in cardiovascular death was 22% in patients with chronic kidney disease (CKD) 3 (eGFR 30 to 59 mL/min) (Wanner et al, 2016 [6]).

The nephroprotective effect is thought to be achieved by mechanisms independent of blood glucose reduction (Rajasekeran et al, 2016 [7]), such as by reduced intra-glomerular pressure through an enhanced tubuloglomerular feedback mechanism (De Nicola, et al 2014 [8] and Thomas, 2014 [9]), reduced glucose and sodium transport over the proximal tubule cells (Pollock, et al 1991 [10] and Komala, et al 2013 [11]),

increased natriuresis (Heerspink et al, 2013 [12]) and reduced systemic blood pressure (Baker et al, 2015 [13]).

Since the sodium/volume related effects are believed to be independent of HbA1c reduction this trial will include both patients with and without T2DM.

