- 13. Ongoing weight-loss diet (hypocaloric diet) or use of weight-loss agents, unless the diet or treatment has been stopped at least 3 months before Screening Visit, ensuring patients having a stable body weight with no verified body weight variability of >3 kg during the 3 months before Screening Visit.

Renal failure-related:

- 14. Symptoms/complaints suggestive of established neurogenic bladder and/or incomplete bladder emptying.
- 15. History of bladder cancer.
- 16. Diagnosis of polycystic kidney disease.
- 17. History of or current lupus nephritis.
- 18. UACR >1000 mg/g per day at the Screening Visit based on spot urine sample (quantitative assessment).
Concomitant Medication and/or study treatment-related:

- 19. Current/chronic use of the following medication: any anti-diabetic medication with the exception of metformin, sulphonylurea, insulin (insulin only allowed in Group 1), oral glucocorticoids, non-steroidal anti-inflammatory drugs (NSAIDs), immune suppressants, chemotherapeutics, antipsychotics, tricyclic antidepressants (TCAs) and monoamine oxidase inhibitors.
- 20. Receiving immunosuppressive or other immunotherapy for primary or secondary renal disease within 6 months prior to Screening Visit (Visit 1).
- 21. Current treatment or treatment within the last 2 weeks prior to Screening Visit (Visit 1) with diuretics including loop diuretics, thiazides, and mineralocorticoid antagonists.
- 22. A metformin dose which is outside the specified dose range for renal impairment according to local guidelines and/or Investigator's judgement.
- 23. Medicinal products and substances that can reduce or increase absorption of indocyanine green: anticonvulsants, bisulphite compounds, haloperidol, heroin, meperidine, metamizol, methadone, morphium, nitrofurantoin, opium alkaloids, phenobarbital, phenylbutazone (reduced absorption), and cyclopropane, probenecid, rifamycin (increased absorption).

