Adverse events (AE), including serious adverse events (SAE) are collected throughout the study, with SAE collection starting at the screening visit and AE collection at dosing, both ending at the last visit (Visit 10, typically day 19). Laboratory safety assessments will generally be done at Screening (Visit 1), Visit 4 and Visit 8 (See Section 5.1.3.2), with some exceptions.

As many of the efficacy measurements will be taken at four distinctive time periods during the course of the study, namely baseline, soon after treatment start, at the end of treatment and at the end of follow up, when reporting the efficacy results of the study each measurement will be assigned to an analysis window:

- **Baseline** is the measurement obtained before initiation of treatment, typically during Visit 4. For 24-hr blood pressure, the baseline measurement is the measurement obtained the day before Visit 4.
- Start of Treatment (ST) is the measurement obtained after the patient has been in the study for a short time, typically on Visit 5.
- End of treatment (ET) is the measurement obtained on the visit corresponding to the last day of the treatment period, namely Visit 8, unless the patient attended an early termination visit. For 24-hr blood pressure, as well as CCI measurements in the 24-hr urine, the end of treatment measurement is the measurement obtained the day before Visit 8.

• Follow-up (FU) is the measurement obtained after the end of the treatment period, namely Visit 9. CC

The exception from the rules outlined above is the 24-hr urine, the collection of which will take place on consecutive days, rather than on one single day. In this case, Baseline, ST, ET and FU used in the analyses will be the averages of these consecutive samples. Explicitly, Baseline is the average of measurements obtained on day -3 to day -1, ST the average of measurements obtained on day 2 to day 4, ET the average of measurements obtained on day 12 to day 14 and FU the average of measurements obtained on day 15 to day 17.

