3. STATISTICAL BASIS FOR SAMPLE SIZE

With a sample size of 15 patients per group and assuming a standard deviation (SD) of 25 milliequivalent (mEq)/24 hours in change from average Baseline in 24-hour sodium excretion, the study will have 80% power to detect an increase of at least 20 mEq/24 hours in average change from average Baseline 24-hour sodium excretion with dapagliflozin within each group at a two-sided alpha level of 0.05.

Under these same conventions for the number of patients, the SD and the alpha level, and assuming 50% power, the minimum detectable difference in change from average Baseline in 24-hour sodium excretion is approximately 13.6 mEq/24 hours.

Similarly, under the same conventions for the number of patients and the alpha level, 50% power and fixing the change from average Baseline in 24-hour sodium excretion to 20 mEq/24 hours, the maximum SD at which statistical significance can be demonstrated is approximately 37 mEq/24 hours.

It is assumed that approximately 10% of the enrolled patients will not provide evaluable data with regards to the primary endpoint, leading to 17 patients to be enrolled in each of the groups. If the non-evaluable rate is higher than expected, additional patients might be enrolled in order to ensure 15 evaluable patients.

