5.3.3 Statistical significance level

All statistical tests will be two-sided and will be performed at the 5% level of significance. No multiplicity adjustments will apply. However, it is acknowledged that the issue of false positives is very relevant in this study, as the number of tested hypotheses is large. This issue

will be taken into consideration when interpreting the results, keeping in mind both the expected number of false positives (i.e. rejections of a hypothesis when no effect is in fact present) and clinical feasibility of the pattern of seemingly detected effects.

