The model for the change between the ET and the FU timepoints will be a linear regression model. This model will be constructed for each group separately and include the baseline value of the studied endpoint as a single covariate. Similarly, to the back-up option for Model 1, the estimated expected change between ET and FU for a patient with an average baseline value, as well as the 95% CI and p-value, will be tabulated.

This will be done using the following SAS code:

```
PROC MIXED DATA = <DATA>;
BY <GROUP>;
CLASS <GROUP>;
MODEL <CHANGE> = <BASE> <GROUP>;
LSMEANS <GROUP> / CL ALPHA = 0.05;
RUN;
```

Here, <CHANGE> refers to the change between ET and FU.

The approach described above will be applied for the analyses of all endpoints, with the exception of PK (discussed separately in Section 5.3.16.5).

The formal analyses will be accompanied by listings, tables with summary statistics and Box plots. The summary tables for the values observed at each measurement timepoint will be presented for each group separately, in general including mean n, SD, median, minimum, maximum, as well as the first and third quartiles. For the change from baseline, the summary will include n, median, minimum and maximum.

5.3.16.2 24-hour urine data

A listing of urine sample collection, showing each collection day's start and stop date/time, urine sodium amount excreted, urine glucose concentration, urine glucose amount excreted, urine volume and UACR, will be presented.

A separate listing will be presented showing the by-patient arithmetic mean of the urine sodium amount excreted, urine glucose amounts excreted urine volume and UACR taken across the following summary periods:

- Baseline: Day -3 up to and including Day -1;
- Start of Treatment (ST): Day 2 up to and including Day 4 and for UACR ST: Day4;
- End of Treatment (ET): Day 12 up to and including Day 14;
- Follow-up (FU): Day 15 up to and including Day 17.

The following by-patient changes will be derived for each urine sodium amount excreted, urine glucose amount excreted, urine volume and UACR:

- ST average versus the BL average
- ET average versus the BL average;
- FU average versus the ET average.

Changes in urine sodium amount excreted, urine glucose amount excreted, urine volume and UACR will be listed, for each of the change types specified above.

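### UACR is modelled as raw mg/g change with raw baseline as covariate; if UACR is skewed, the planned test rejects a true null too often, so it should be analysed on the log scale.

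*SAP*

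**What the plan says.** SAP 5.3.16.1 defines Model 1 as a repeated-measures model for change from baseline, with time, raw baseline and their interaction as fixed effects and an unstructured covariance. Model 2 regresses the change from end of treatment to follow-up on raw baseline. On scope it says: "The approach described above will be applied for the analyses of all endpoints, with the exception of PK". Protocol 8.3.2 likewise applies the primary model to the secondary endpoints, and UACR is one of these (Protocol 3.2.2, SAP 5.1.5.2).

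SAP 5.3.16.2 forms each period value for UACR as an arithmetic mean. Geometric statistics appear only for dapagliflozin and indocyanine green concentrations. Eligibility sets an upper limit, excluding patients with "UACR >1000 mg/g per day at the Screening Visit based on spot urine sample", and no lower one. The protocol background gives the expected effect as a proportion: "reduction around 40% in albuminuria".

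On error control, SAP 5.3.3 says "All statistical tests will be two-sided and will be performed at the 5% level of significance" and "No multiplicity adjustments will apply".

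The early UACR value is described in two ways. SAP 5.3.16.2 has "Day 2 up to and including Day 4 and for UACR ST: Day4". SAP section 2, writing of 24-hour urine without exception, has "ST the average of measurements obtained on day 2 to day 4".

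**The concern.** A group that may run from normal albuminuria to 1000 mg/g is likely to have a long right tail, and a drug effect on albuminuria is usually thought of as a percentage. If changes are proportional, the spread of the mg/g change grows with baseline. Model 1 assumes the same error variance for every patient at a given time and regresses on the very variable that drives the spread. The patient with the highest baseline pulls the slope towards their own error, the residual variance comes out too small, and the CI at mean baseline is too narrow.

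At stake are the CI and p-value for a secondary endpoint tied to the kidney-protection rationale. A reader would take the p-value as a 5% test when its true size could be well above that.

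**Working it through.** **1. The plan's own figure.** The only sample-size calculation is for sodium: "With a sample size of 15 patients per group and assuming a standard deviation (SD) of 25 milliequivalent (mEq)/24 hours", with a difference of 20 mEq/24 h. For a one-sample t-test the noncentrality is 20/(25/√15) = 3.10 on 14 df, which gives power 82.1% (79.0% at n = 14). So 15 is the smallest n that reaches 80%, and 15/0.9 = 16.7, rounded up to 17. At 50% power the minimum detectable difference is 13.59 and the maximum SD 36.8, matching the stated 13.6 and 37. The plan reproduces, but it has no corresponding figure for UACR.

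**2. What Model 1 computes.** With complete data and the same baseline covariate at both times, the unstructured REML fit gives the same least-squares mean and SE as a separate regression at each time, evaluated at mean baseline. A numerical check on one data set agreed (SEs 0.0807 and 0.1772 by both routes). The estimate is the mean change, with SE² = s²/n and s² = RSS/(n−2).

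**3. Why the SE is too small.** Write the change as D = B(R−1), with baseline B and ratio R. Then Var(D|B) = B²·Var(R). With patient variances v and leverages h:

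- true variance of the mean: Σv/n²
- expected planned estimate: Σv(1−h)/[n(n−2)]
- ratio of planned to true: [n/(n−2)] × the average of (1−h), weighted by v

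Large v coincides with large h. At between-patient log-SD 1.0-1.5 the median highest leverage is about 0.45-0.66. In the limiting case where that one patient carries all the error variance, the ratio is (15/13)(0.55) = 0.63 down to (15/13)(0.34) = 0.39. The SE is then √0.63 = 0.80 down to √0.39 = 0.63 of its true value. Real data would be less extreme.

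**4. Simulated size.** All UACR inputs here are assumptions: lognormal, capped at 1000 mg/g, median 20-300 mg/g, n = 15, with several levels of within-patient noise. The test is two-sided at 5%, under no effect.

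| Between-patient log-SD | Planned test rejects |
|---|---|
| 0.5 | about 7-11% |
| 1.0 | 9-17% |
| 1.5 | 11-23% |
| 2.0 | 13-27% |

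The log-scale model with ln(baseline) rejects in 4.5-7.3% over all scenarios, and in about 5-6% once log-SD is 1 or more.

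**5. Simulated power of the planned, baseline-adjusted test.**

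| Scenario | Planned, nominal | Log scale | Planned, corrected to true 5% size |
|---|---|---|---|
| 25% reduction, log-change SD 0.4 | 51-54% | 73% | not computed |
| 25% reduction, log-change SD 0.25 | 83-93% | 98% | not computed |
| 25%, end of treatment, noise 0.2 per period and 0.3 per day | 68-75% | about 79% | 33-62% |
| 40%, same noise | 94-98% | 99.8% | 70-96% |
| 25%, end of treatment, noise 0.3 per period and 0.4 per day | 52-56% | 49-52% | 21-38% (log 47-49%) |

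In the last row the raw test appears to do as well or better, but only because its size is inflated.

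**6. Influence.** At log-SD 1.0-1.5 the largest single change is about 21-38% of the summed absolute change among 15 patients, and the two largest about 36-59%.

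**7. Early UACR value.** Protocol 3.2.2 and SAP 5.1.5.2 both define the early endpoint as average Baseline to Day 4. SAP 5.3.16.2 implements this in its period definition, but its list of changes still describes the early change for UACR as a period average. SAP section 2 gives Days 2-4 for all 24-hour urine.

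**The case against.** The best defence is that the documents contain no UACR mean, SD or distribution. The 1000 mg/g limit is a cap, and the SAP's descriptive UACR bands include one from 2200 mg/g upwards, above that cap, so they do not describe this population. This stands: any single error rate, such as 15-24%, cannot be derived from the documents, and at log-SD 0.5 the excess is modest.

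Three stronger readings are tempting and not supported:

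- **Power collapses.** An unadjusted t-test on raw change gives 23-35% power against 73-74% on the log scale in the log-change SD 0.4 setting. The SAP does not plan that test; it is baseline-adjusted, and the loss is smaller.
- **Most patients contribute almost nothing.** If the two largest changes make up 36-59% of the total, the other 13 still supply 41-64%.
- **Day 4 alone is a mistake.** A 3-day early mean would cut the SE by about 29%, since √[(2/3)/(4/3)] = 0.71. That assumes independent daily noise and a constant effect over Days 2-4, and Day 4 is the pre-specified endpoint in both documents. Replacing it would need a protocol change.

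Mitigation exists. UACR is one secondary endpoint in an uncontrolled mechanistic study, and medians, ranges, box plots and listings would expose an outlier. But these are descriptive; the CI and p-value come from the raw model. SAP 5.3.3 promises caution about false positives because many hypotheses are tested, not because one test exceeds its nominal size. Parts of the SAP are redacted, so a transformation stated there cannot be excluded, but the visible general rule covers UACR.

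**Conclusion.** The concern holds as a conditional one. The plan analyses UACR untransformed, and if UACR is skewed with roughly proportional changes, the planned CI and p-value are unreliable. Under assumed lognormal UACR with 15 patients per group, the false-positive rate is about 7-27%, rising with skewness, against about 5-7% on the log scale. Nominal power is lower than on the log scale in most scenarios; where it is not, inflated size explains it. One or two patients can dominate the estimate; that they will is not established. On the early value, the only defect is inconsistent wording within the SAP. The change should be made, but the primary sodium result does not depend on it.

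**What to change.** In SAP 5.3.16.1-5.3.16.2, specify for UACR:

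- Average the daily ln(UACR) values within each period. Taking the log of a 3-day arithmetic baseline and comparing it with a single Day 4 log value would add a small downward bias.
- Fit Models 1 and 2 to the change in ln(UACR), with ln(baseline) as covariate.
- Back-transform to a geometric mean ratio, shown as percent change with 95% CI, and keep the raw mg/g result as supportive.
- Keep Day 4 as the early endpoint. Optionally add the Day 2-4 mean as supportive; the protocol's study-plan footnotes already have UACR measured on every collection day.
- State the UACR exception in SAP section 2 and correct the list of changes in 5.3.16.2.

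The cost is SAP wording and a transform, with no new data or visits. Results reported below an assay limit are already set to the limit (SAP 5.3.6), so the log of such values is defined. The one small downside is that the main estimate becomes a percent change rather than mg/g.

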5.3.16.4 Measurements for plasma volume estimates

The total plasma volume will be estimated based on results from a noncompartmental analysis of the plasma ICG-time profile. The derivation of the plasma volume estimates will be conducted by AstraZeneca and details regarding the estimation techniques will be documented separately. The plasma volume estimates will be provided to PAREXEL for further analysis and reporting as described below.

Presentation of ICG

The bolus dose of ICG (in mg) administered will be derived based on the administered volume (mL) and the confirmed strength (5 mg/mL) of the ICG solution:

• bolus dose administered (mg) = volume administered (mL) x 5 mg/mL.

The details of the bolus dose of ICG administered for each study day will be listed, including the dose volume and the date/time of the ICG injection and bolus dose.

The plasma ICG concentrations will be listed by patient and time-point, including the date/time of the sample; and will be summarised using geometric mean, 10th and 90th percentiles by group and time-point.

Presentation of plasma volume

Changes in the estimated plasma volume will be derived. The following changes will be calculated:

- Change from baseline (Day 1, pre-dose) to ST (Day 4);
- Change from baseline to ET (Day 14);
- Change from ET (Day 14) to FU (Day 18).

The estimated plasma volume for each patient and study day will be listed and summarised by study period and group, including changes specified above. Box plots for the estimated plasma volume versus study period by group will be presented.

5.3.16.5 Pharmacokinetic concentrations

All PK presentations will be based on all available data.

A listing of PK blood sample collection times, as well as derived sampling time deviations will be provided. In addition, plasma concentrations of dapagliflozin will be listed by patient and time-point.

Plasma dapagliflozin concentrations will be summarised by group and time-point. Where possible, the following descriptive statistics will be presented: n, geometric mean, [geometric mean x geometric SD], [geometric mean / geometric SD], geometric CV%, median, minimum and maximum.

In all cases, the geometric mean is calculated as follows:

• Geometric mean = $\exp[M_L]$,

where M_L is the mean of natural log-transformed values, and 'exp' refers to the natural exponential function.

The geometric CV% is calculated as follows:

• Geometric CV% = $100 \text{ x sqrt}[\exp(S_L^2) - 1]$,

where S_L is the SD of natural log-transformed values, and 'sqrt' refers to the square root function.

The geometric SD is calculated as follows:

• Geometric SD = $\exp[S_L]$,

where S_L is defined as above.

The PK profiles will also be illustrated by figures for average PK profile over time on a linear and a semi-logarithmic scale.

5.3.16.6 Censored data for pharmacokinetic evaluation

For the listings, plasma concentrations that are NQ will be listed as "BLQ" – no imputations or substitutions will be performed for the listings. For descriptive statistics, plasma concentrations that are NQ will be handled as described below.

Any dapagliflozin plasma concentration data reported as not quantifiable (NQ), below the limit of quantification (BLQ), "<x.xx" or similar will be handled as follows for the descriptive statistics:

- At a time-point where less than or equal to 50% of the values are NQ, all NQ values will be set to the lower limit of quantification (LLOQ), and all descriptive statistics will be calculated.
- At a time-point where more than half of the values (but not all) are NQ, the geometric mean, [geometric mean x geometric SD], [geometric mean / geometric SD] and geometric coefficient of variation (CV)% will be set to Not Determined ("ND"). The maximum value will be reported from the individual data, and the minimum and median will be shown as "BLQ" below the limit of quantification.
- If all values are NQ at a time-point, no descriptive statistics will be calculated for that time-point. Not applicable ("NA") will be written in the field for geometric CV% and "BLQ" will be written in all other statistics.
- The number of BLQ values (n below LLOQ) and the number of data points (n) will be reported for each time-point.

5.3.16.7 Bioimpedance spectroscopy

The BIS examination will consist of two parts: an evaluation at Baseline, ST, ET and FU, similar to other efficacy endpoints, and acute changes evaluation at ET, aiming to examine the changes between a pre-dose measurement and measurements 1, 2 and 4 hours post-dose. The measurements obtained during BIS, and for which the analyses will be performed, are CCI, extracellular fluid (in litre and %), CCI

Part 1

[figure not shown]
Changes in the BIS results will be derived. The following changes will be calculated:

- Change from Baseline (Day 1, pre-dose) to ST (Day 4);
- Change from Baseline (Day 1, pre-dose) to ET (Day 14, 1 h post-dose);
- Change from ET (Day 14, 1 h-post-dose) to FU (Day 18).

The BIS results for each patient, as well as corresponding changes, will be listed. Results will also be summarised by time-point and group, including changes specified above, similarly to other efficacy endpoints.

Corresponding box plots for the BIS results versus study period will be presented, with each group overlaid on the same plot. The statistical model from Section 5.3.16.1 will be used to analyse the changes more formally, with results presented as described in Section 5.3.16.1.

Following variables will also be listed:

• Systolic daily average, CCI

AstraZeneca D1690C00049 Final 3.0 25 Oct 2019 Diastolic daily average, CCI

CCI

- Plasma volume
- Extracellular fluid (litres and percent), CCI
- 24-hr urinary volume
- Sodium excretion (24-hr urine)

